7.3 Derivation of CTCAE Grade – Hematological Tests

Tests	Direction	Grade			
		1	2	3	4
Hemoglobin (g/dL, ↓ mmol/L or g/L)	<LLN - 10.0 g/dL; <LLN - 6.2 mmol/L; <LLN -100 g/L	<10.0 - 8.0 g/dL; <6.2 - 4.9 mmol/L; <100 - 80g/L	<8.0 g/dL; <4.9 mmol/L; <80 g/L;	<8.0 g/dL; <4.9 mmol/L; <80 g/L;	Life-threatening consequences;
Platelet (/mm ³ or ↓ /L)	<LLN - 75,000/mm ³ ; <LLN - 75.0 x 10 ⁹ /L	<75,000 - 50,000/mm ³ ; -50.0 x 10 ⁹ /L	<75,000 - 50,000/mm ³ ; -25.0 x 10 ⁹ /L	<50,000 - 25,000/mm ³ ; -25.0 x 10 ⁹ /L	<25,000/mm ³ ; <25.0 x 10 ⁹ /L
Neutrophils (/mm ³ ↓ or /L)	<LLN - 1500/mm ³ ; <LLN - 1.5 x10 ⁹ /L	<1500 - 1000/mm ³ ; <1.5 - 1.0 x10 ⁹ /L	<1000 - 500/mm ³ ; <1.0 - 0.5 x10 ⁹ /L	<1000 - 500/mm ³ ; <1.0 - 0.5 x10 ⁹ /L	<500/mm ³ ; 10 ⁹ /L
Lymphocyte (/mm ³ ↓ or /L)	<LLN - 800/mm ³ ; <LLN - 0.8 x10 ⁹ /L	<800 - 500/mm ³ ; <0.8 - 0.5 x10 ⁹ /L	<500 - 200/mm ³ ; <0.5 - 0.2 x10 ⁹ /L	<200/mm ³ ; <0.2 x 10 ⁹ /L	

Note: 10⁹ = 10⁹; LLN = Lower Limit of Normal; ULN = Upper Limit of Normal

PAREXEL International
 Statistical Analysis Plan Template for Early Phase Studies

Symphegen A/S
 Sym013-01

7.4 Derivation of CTCAE Grade – Clinical Chemistry Tests

Tests	Direction	Grade			
		1	2	3	4
Sodium (mmol/L)	↓	<LLN - mmol/L	130 -	<130 - 120 mmol/L	<120 mmol/L
Sodium (mmol/L)	↑	>ULN - mmol/L	150	>155 - 160 mmol/L	>160 mmol/L
Potassium (mmol/L)	↓	<LLN - 3.0 mmol/L	-	<3.0 - 2.5 mmol/L	<2.5 mmol/L
Potassium (mmol/L)	↑	>ULN - 5.5 mmol/L	>5.5 - 6.0 mmol/L	>5.5 - 6.0 mmol/L	>7.0 mmol/L
Glucose	↓	<LLN - 55 mg/dL; <LLN - 3.0 mmol/L	<55 - 40 mg/dL; <3.0 - 2.2 mmol/L	<40 - 30 mg/dL; <2.2 - 1.7 mmol/L	<30 mg/dL; <1.7 mmol/L
Glucose	↑	Fasting glucose value >ULN - 160 mg/dL; Fasting glucose value >ULN - 8.9 mmol/L	Fasting glucose value >160 - 250 mg/dL; Fasting glucose value >ULN - 8.9 mmol/L	>250 - 500 mg/dL; >13.9 - 27.8 mmol/L	>500 mg/dL; >27.8 mmol/L
Creatinine	↑	>1 - 1.5 x baseline; >ULN - 1.5 x ULN	>1.5 - 3.0 x baseline; >1.5 - 3.0 x ULN	>3.0 baseline; >3.0 - 6.0 x ULN	>6.0 x ULN
Bilirubin	↑	>ULN - 1.5 x ULN	>1.5 - 3.0 x ULN	>3.0 - 10.0 x ULN	>10.0 x ULN
Alkaline phosphatase (AKP)	↑	>ULN - 2.5 x ULN	>2.5 - 5.0 x ULN	>5.0 - 20.0 x ULN	>20.0 x ULN
AST (SGOT)	↑	>ULN - 3.0 x ULN	>3.0 - 5.0 x ULN	>5.0 - 20.0 x ULN	>20.0 x ULN
ALT (SGPT)	↑	>ULN - 3.0 x ULN	>3.0 - 5.0 x ULN	>5.0 - 20.0 x ULN	>20.0 x ULN
Uric Acid	↑	>ULN - 10 mg/dL (0.59 mmol/L)	-	-	>10 mg/dL; >0.59 mmol/L
Calcium	↑	Corrected serum	Corrected serum	Corrected serum	Corrected serum

PAREXEL International
Statistical Analysis Plan Template for Early Phase Studies

Sympheogen A/S
Sym013-01

Tests	Direction	Grade			
		1	2	3	4
		calcium of Hypercalcemia >ULN mg/dL; >ULN mmol/L; Ionized calcium >ULN - 1.5 mmol/L	calcium of >11.5 - 12.5 mg/dL; >2.9 - 3.1 mmol/L; Ionized calcium >1.5 - 1.6 mmol/L	>12.5 - 13.5 mg/dL; >3.1 - 3.4 mmol/L; Ionized calcium >1.6 - 1.8 mmol/L	>13.5 mg/dL; >3.4 mmol/L; Ionized calcium >1.8 mmol/L
Calcium	↓	Corrected serum calcium of <LLN - 8.0 mg/dL; <LLN mmol/L; Ionized calcium <LLN -1.0 mmol/L	Corrected serum calcium of <8.0 - 7.0 mg/dL; <2.0 - 1.75 mmol/L; Ionized calcium <1.0 - 0.9 mmol/L	Corrected serum calcium of <8.0 - 7.0 mg/dL; <2.0 - 1.75 mmol/L; Ionized calcium <1.0 - 0.9 mmol/L	Corrected serum calcium of <6.0 mg/dL; <1.5 mmol/L; Ionized calcium <0.8 mmol/L;
Phosphate	↓	<LLN - 2.5 mg/dL; <LLN - 0.8 mmol/L	<2.5 - 2.0 mg/dL; <0.8 - 0.6 mmol/L	<2.0 - 1.0 mg/dL; <0.6 - 0.3 mmol/L	<1.0 mg/dL; <0.3 mmol/L

Note: 10^{9} = 10⁹; LLN = Lower Limit of Normal; ULN = Upper Limit of Normal

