7.2 Other Drugs to be Used in the Trial

7.2.1 Pre-Medication for Pan-HER Infusion-Related Reactions

There is an inherent risk for IRRs with the administration of mAbs. A premedication schedule will therefore be implemented for all patients treated.

For Part 1, premedication is mandatory prior to each dose of Pan-HER.

For Part 2, premedication is mandatory prior to each dose of Pan-HER during Cycle 1 and 2.

As of Amendment 5, all patients must be premedicated as described with standard therapies that include each of the following. The recommended premedication doses are as follows:

- Montelukast (selective leukotriene receptor antagonist) 10 mg PO daily × 7 prior to each Pan-HER infusion (schedule may be extended to daily throughout study at the Investigator's discretion); plus approx. 0.5 hours prior to the start of Pan-HER infusion
- Dexamethasone 10 mg PO, approx. 12 and 6 hours prior to the start of Pan-HER infusion
- Glucocorticoid therapy equivalent to 80-100 mg IV methylprednisolone, approx. 0.5 to 2 hours prior to the start of Pan-HER infusion
- Antihistamine (H1 antagonist) equivalent to 25-50 mg IV diphenhydramine, approx. 0.5 hours prior to the start of Pan-HER infusion
- Antihistamine (H2) antagonist such as 50 mg IV ranitidine or 30 mg famotidine, approx. 0.5 hours prior to the start of Pan-HER infusion

Confidential Page 66 of 156

 Acetaminophen such as 1000 mg IV or PO (orally), approx. 0.5 hours prior to the start of Pan-HER infusion

In Part 2, if a patient is without evidence of IRRs after Cycle 2, the Investigator may choose to withdraw premedication on a patient-by-patient basis with subsequent dosing in order to determine whether such continued therapy is necessary in that patient. Where practical, it is recommended that withdrawal of premedication be done in a gradual fashion.

For those patients who experienced symptoms suggestive of an IRR after Cycle 1, consideration should be given to continuing premedication for at minimum 1 to 2 additional doses before any future attempt to withdraw.

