8.2.9 Laboratory Assessments and Pregnancy Test

All routine laboratory analyses will be performed at a laboratory facility local to the trial site.

Sponsor or designee must be provided with trial site laboratory normal ranges for all required parameters prior to screening of the first patient at the site. Likewise, any change in laboratory normal ranges during the trial should be forwarded to the Sponsor or designee promptly during the trial.

Blood samples will be taken at the scheduled visits and analyzed for the following parameters as per **Table 10** and as clinically indicated. Results must be available and assessed prior to dosing of Pan-HER, when sampling is scheduled on days of dosing. All individual assessments are to be performed on or about the indicated visit day (i.e., ± 2 days) unless otherwise stated.

Table 10 Schedule of Safety Blood and Urine Samples

Sample Analysis	Screening		Cycl	le 1		Cycles Thereafter		ЕОТ	1M FUP
Day within Cycle		D1	D3 D8	D15	D22	D1	D15		
Hematology Panel	X	X^1	X	X	X	X	X	X	X
Biochemistry Panel	X	X^1	X	X	X	X	X	X	X
Coagulation Panel	X	X^1		X		X		X	X
Urinalysis	X	X^1		X		X		X	X
Pregnancy Test	X							X	

Abbreviations (in alphabetical order): D, day; EOT, End of Treatment Visit; 1M FUP, 1-Month Follow-up Visit

1) Does not need to be performed prior to C1/D1, if performed during screening ≤7 days from C1/D1

Confidential Page 75 of 156

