8.2.9.2 Biochemistry Panel

To include sodium, potassium, chloride, bicarbonate or carbon dioxide, blood urea nitrogen (BUN), creatinine, glucose, bilirubin [total and direct], AST, ALT, ALP, calcium, magnesium, phosphorus, albumin, total protein, uric acid, amylase, lipase, and creatine kinase (fasting not required). Clinically significant electrolyte abnormalities should be corrected prior to dosing.

- Screening
- Cycle 1
 - Weekly (prior to dosing if on dosing days)

Note: Does not need to be performed prior to C1/D1, if performed during screening ≤ 7 days from C1/D1.

- o Day 3
- Each cycle thereafter
 - o Day 1 and 15 (prior to dosing)
- EOT
- 1M FUP

Confidential Page 76 of 156

As clinically indicated

In the event of significant biochemistry abnormalities, the evaluation frequency should be increased to include additional evaluations between the scheduled assessments, as clinically indicated. In the event of creatine kinase abnormalities, isoenzyme analysis should be performed.

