4.11.4 Clinical Laboratory Evaluation

All clinical laboratory test results will be presented and summarized using the International System of Units (SI units; Système International d'Unités). The original lab test units will be converted to SI according to *Young, D.S and Huth, E.J; 1998; SI Units for Clinical Measurement; American College of Physicians; Philadelphia and Burtis, C.A, Ashwood, E.R and Bruns, D.E; 2008; Fundamentals of Clinical Chemistry; Saunders Elsevier; Missouri* [Laboratory test converted to SI will be stored in SDTM LB domain as LBSTRESU and LBSTRESC]. Additionally, clinical laboratory test results will be converted in Conventional Units, and store in SDTM SUPPLB domain.

All clinical laboratory test results will be graded per NCI CTCAE v4.03 if applicable, as well as high (higher than the normal range), normal (in the normal range) and low (lower than normal range).

Descriptive statistics (n, mean, standard deviation, median, and range) of the lab parameters and changes from baseline will be presented by regimen and dose group for biochemistry, hematology, and coagulation. Such descriptive statistics will be presented at Baseline and at End of Study, as well, Worst Result post Baseline (i.e. Maximum and Minimum post Baseline including results from unscheduled assessments) will be presented as well.

Shift in biochemistry, hematology, and coagulation result CTCAE grading from baseline will be tabulated at the end of treatment, as well as from baseline to the maximal grade during the study (maximal grade will also include results from unscheduled and repeated assessments).

PAREXEL International
Statistical Analysis Plan Template for Early Phase Studies

Symphegen A/S
Sym013-01

All clinical laboratory test results will be listed in the original, SI, and Conventional units, for biochemistry, hematology, coagulation, and urinalysis.

Individual patient biochemistry, hematology, and coagulation parameters during the trial can be presented graphically using longitudinal spaghetti plots. Specific lab parameters to be plotted will be decided by Symphegen from clinical meaning perspective after examination of corresponding listings.

Biochemistry, hematology, and coagulation parameters will be presented using box plots by visits and tumor type.

Results from the pregnancy tests will be listed.

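### SAP 7.4 defines Grade 1-2 high glucose on fasting values, but the protocol does not require fasting samples, so the Grade 1-2 glucose cells of Table 14.3.5.5 cannot be validly derived

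*SAP*

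**What the plan says.** SAP 7.4 sets out the CTCAE derivation for high glucose. Grade 1 is "Fasting glucose value >ULN - 160 mg/dL; Fasting glucose value >ULN - 8.9 mmol/L" and Grade 2 begins "Fasting glucose value >160 - 250 mg/dL". Grade 3 is ">250 - 500 mg/dL; >13.9 - 27.8 mmol/L" and, like Grade 4, has no fasting condition.

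Protocol 8.2.9.2 lists glucose in the biochemistry panel, and that list ends "amylase, lipase, and creatine kinase (fasting not required". SAP 3.2.4.3 repeats the panel without the remark on fasting.

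SAP 4.11.4 grades all laboratory results where CTCAE applies and classifies them as high, normal or low. It tabulates the grade shift from baseline to end of treatment, "as well as from baseline to the maximal grade during the study", with unscheduled and repeat values included. Table 14.3.5.5 (chemistry) carries the asterisk that keeps it in the abbreviated report.

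On sampling and premedication, Protocol 8.2.9 states: "Results must be available and assessed prior to dosing of Pan-HER, when sampling is scheduled on days of dosing". As of Amendment 5, Protocol 7.2.1 includes in the mandatory premedication "Dexamethasone 10 mg PO, approx. 12 and 6 hours prior to the start of Pan-HER infusion", plus an intravenous glucocorticoid 0.5 to 2 hours before the infusion.

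**The concern.** The grading rule needs a fact about each sample that the protocol does not secure. If fasting status is unknown, a value between the ULN and 250 mg/dL cannot be placed in Grade 1 or 2, or excluded from them, by the SAP's own definition. The row would then reflect an undocumented programming choice. Protocol 7.2.2.2 names hyperglycaemia among the potential toxicities of anti-HER drugs that regular blood samples are meant to assess, so someone will read this row for a signal.

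A second matter affects interpretation at every grade. A sample drawn on a dosing day may follow glucocorticoid premedication, and nothing in the planned table tells the reader so.

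**Working it through.** No sample size or error rate is involved. The check is a comparison of texts, with one unit conversion.

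**1. Units.** The SAP's own pairs give 160 / 8.9 = 17.98 and 500 / 27.8 = 17.99 mg/dL per mmol/L. Hence 250 mg/dL is 250 × 27.8 / 500 = 13.9 mmol/L. Grades 1 and 3 are internally consistent, and Grade 2 in SI units should run from above 8.9 to 13.9 mmol/L.

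**2. What happens to a value of unknown fasting status.** There are two ways to program SAP 7.4 and 4.11.4:

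| Value | Fasting condition ignored | Fasting condition enforced |
|---|---|---|
| Above ULN to 160 mg/dL | Grade 1 | no grade |
| Above 160 to 250 mg/dL | Grade 2 | no grade |
| Above 250 to 500 mg/dL | Grade 3 | Grade 3 |
| Above 500 mg/dL | Grade 4 | Grade 4 |

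The two readings differ over the whole range from ULN to 250 mg/dL and agree above it. Ignoring the condition applies a fasting threshold to samples that may follow a meal. Enforcing it leaves those values out.

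**3. What no grade means in the table.** Under the second reading, a patient whose post-baseline values all lie at or below 250 mg/dL could be shown as Grade 0 or dropped as missing. SAP 4.2 takes percentages over patients providing data, so this choice also changes the denominator. The SAP does not make it.

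**4. Baseline.** SAP 4.2 takes the last pre-treatment value, with no fasting condition. The baseline side of the shift therefore has the same defect.

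**5. Steroid timing.** Oral dexamethasone is due about 12 and 6 hours before the infusion, and the sample comes before the infusion, so it can follow one or both doses. It need not:
- Protocol 8.2.9 allows about 2 days either side of the visit.
- Day 3, Q2W Days 8 and 22, end of treatment and the 1-month follow-up are not dosing days.
- Protocol 8.2.9.2 allows a screening sample within 7 days to replace the C1/D1 sample. The baseline may therefore precede dexamethasone in one patient and follow it in another.

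Protocol 3.2.4.1 gives 1 + 1 + 4 + 3 + 7 + 3 = 19 patients entered by Amendment 6. Of these, 19 − 3 = 16 entered before the current list was mandatory. They already had required glucocorticoid premedication, and oral dexamethasone was recommended part-way through the 9 mg/kg Q2W cohort. The levels with mandatory prophylaxis (+ P) therefore differ from the earlier ones in steroid intensity. It is not a contrast of steroid against none.

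**6. The Grade 2 SI limits.** In the text available here, the Grade 2 mmol/L entry repeats the Grade 1 limits (above ULN to 8.9). If the original reads the same, values above 8.9 and up to 13.9 mmol/L have no grade in SI units, and SAP 4.11.4 summarises in SI units. Neighbouring rows of the table also show repeated cells, so this may be an artefact of reading the PDF.

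**The case against.** The strongest reply is that SAP 4.11.4 grades results only where CTCAE applies and that SAP 7.4 itself restricts Grades 1-2 to fasting values. Read literally, non-fasting values receive no Grade 1-2, which is close to the remedy proposed here. The eCRF cited in SAP 1 might also record fasting status; it is not available for review. This part stands: it cannot be said that the table will grade meals as toxicity. It does not remove the problem. The SAP does not state the strict reading, does not say how ungraded values are counted, and would leave a reader taking empty Grade 1-2 cells as absence of mild hyperglycaemia.

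A reader might go further and infer three things that the documents do not support:

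- **A large, quantifiable excess of Grade 1-2 patients.** Any percentage needs an assumed chance per draw of a value above ULN and an assumption about correlation between a patient's draws. The documents give neither.
- **Inflation of the shift at every level.** Baseline can be non-fasting too, and can follow dexamethasone, so the direction may vary by patient.
- **A spurious dose-related effect.** SAP 3.1 lists + P and non-P as separate dose levels, and SAP 4.2 already tabulates by dose group. The 9 mg/kg Q2W level exists in both forms, and 6 mg/kg exists as Q2W without P and as Q1W with P. Earlier cohorts also received glucocorticoid.

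It is also fair to say that the stakes are limited. Safety reporting is descriptive, and Protocol 9.1.3 names no adverse events of medical interest. A laboratory value becomes an adverse event only under the conditions of Protocol 9.1.2, and for glucose the DLT definition starts at Grade 3.

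**Conclusion.** The conflict is real and neither document resolves it. Grade 1-2 high glucose cannot be validly derived from samples not documented as fasting, and non-fasting values up to 250 mg/dL may be misgraded or left uncounted. Grades 3 and 4 are free of the fasting problem, though not of a possible steroid effect.

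The size is modest: one analyte, two grades, in a descriptive shift table that is retained for the report. No DLT or MTD rule depends on it. The conclusion assumes that fasting status is not captured in the eCRF; if it is, samples documented as fasting can be graded as written. It needs no assumption about how often patients had eaten.

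**What to change.** In SAP 7.4 and 4.11.4, state that Grade 1-2 high glucose is not derived from samples not documented as fasting. For glucose in Table 14.3.5.5, show Grades 3-4 only, together with the high/normal/low classification that SAP 4.11.4 already plans.

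Add a footnote saying that samples were not required to be fasting and that dosing-day samples may follow glucocorticoid premedication, more intensive in the + P levels. It should add that both can affect all grades and the flag. The flag is retained because it makes no claim about grade, not because it is free of these influences. No change to the display of + P and non-P levels is needed.

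Before programming, check the Grade 2 mmol/L entry against the original SAP and correct it if it repeats the Grade 1 limits.

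The cost is a sentence, a footnote and a small change to one table. The downside is that there will be no Grade 1-2 glucose counts. The observed values remain in Table 14.3.5.2 and Listing 16.2.8.2.
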